In this study that included over 3600 in-person assessments of pulse oximetry monitoring status, we found that the overall monitoring rate across all hospitals was 46%, with a very wide range of variation, ranging from hospitals that monitor $<5\%$ of these patients to hospitals that monitor $>85\%$ of these patients (results not yet published; see figure below). These results support efforts to reduce continuous pulse oximetry in stable bronchiolitis patients in outlier hospitals with high use rates.

Prior to submitting a subsequent grant that will aim to de-implement continuous pulse oximetry in a well-defined stable bronchiolitis population, we must establish the feasibility of a foundational audit and feedback strategy for addressing continuous pulse oximetry overuse.

Continuous pulse oximetry overuse rates (by hospital, unadjusted, with 95% CIs)

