8.4.1.2 Plan for proactive surveillance for threats to patient safety

In this study, we will regularly evaluate the safety of the intervention, since the intervention may lead to less intensive monitoring for some bronchiolitis patients. In order to monitor for threats to safety, we will:

- Monitor for code blue team activations and rapid response team / medical emergency team / critical assessment team activations in all bronchiolitis patients hospitalized on units participating in the study during the intervention period. This includes patients who were not subjects of data collection, because the intervention is applied at the unit level and could impact the care of patients with bronchiolitis even if they are not reviewed during data collection rounds.
- Investigators will review the chart of each patient meeting the above criteria to determine if the patient was unmonitored at the time of the event that led to the activation.
- Events meeting the activation criteria in which the patient was unmonitored at the time of the event that led to the activation will be considered study adverse events, whether or not they

are related to the research intervention, and be documented in research records as meeting those criteria.

- Investigators will then determine, through chart review and speaking with staff present at the time of the event, if available, if the event was at least possibly related to the study intervention, defined as “there is a reasonable possibility that the adverse event may have been caused by the procedures involved in the research.”
- Investigators will follow the CHOP IRB’s Unanticipated Problems Decision Tree (<https://irb.research.chop.edu/unanticipated-problems>) in order to determine whether the Adverse Event requires prompt reporting to the IRB or should be filed with the next continuing review.
- Adverse Events that meet the definition of Unanticipated Problem Involving Risks to Subjects will be reported promptly to the IRB and the study will be suspended pending review of the event by the IRB. Following the review, we will work with the IRB and staff from the inpatient units to determine if the study should be modified to improve the safety of patients.
- Sites other than CHOP will follow their IRB’s internal reporting requirements, if they differ from the procedures outlined above.

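### Only activations in unmonitored children must be documented and assessed for relatedness, so the safety count would rise as monitoring falls even at unchanged risk, and no total is required beside it

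*Combined protocol and SAP*

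**What the plan says.** Section 8.4.1.2 describes a chain of steps. It gives as the reason for surveillance that the intervention may reduce how intensively some children are monitored.

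- **Ascertainment.** Investigators will "Monitor for code blue team activations and rapid response team / medical emergency team / critical assessment team activations in all bronchiolitis patients" who are "hospitalized on units participating in the study during the intervention period". This includes children never seen on data collection rounds.
- **Chart review.** "Investigators will review the chart of each patient meeting the above criteria to determine if the patient was unmonitored" when the precipitating event occurred.
- **Label and record.** "Events meeting the activation criteria in which the patient was unmonitored at the time of the event that led to the activation" become study adverse events, whatever their cause, and must "be documented in research records as meeting those criteria".
- **Relatedness.** For these events the investigators judge "if the event was at least possibly related to the study intervention", then follow the IRB decision tree. Suspension depends on meeting the definition of an Unanticipated Problem.

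No other section adds a record of activations. They are not among the data elements in sections 5.2 and 5.3, the endpoints in 6.1 and 6.2, or the methods in 6.3. Section 7.1 refers back to 8.4.1. Section 7.2 covers reporting to the IRB and gives no other definition or tabulation.

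Section 5.3 records continuous pulse oximetry and electrocardiographic monitoring as separate items. Section 8.4.1.2 does not say which of them, or whether both, must be absent for a child to count as unmonitored.

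**The concern.** An event is counted only if the child is in the state that the intervention tries to make more common. If children moved off monitors carry any activation risk at all, the count rises as monitoring falls, with no change in safety. Equally, a real fall in total risk could leave the count flat, and a rise among monitored children would not enter the required record.

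The section sets out to evaluate the intervention's safety regularly. A subset whose size depends on uptake cannot support that aim without the total beside it.

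The filter also comes before the relatedness judgement, so careful adjudication cannot recover what it removes. Consider a child found hypoxic at an intermittent check, put back on a monitor, and then worsening until the team is called. With unmonitored undefined and the triggering event open to interpretation, one site could include this child and another could not. Late detection is a harm that less intensive monitoring could plausibly cause.

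**Working it through.** The plan gives no activation rate, expected adverse event count or safety threshold, so there is no stated figure to reproduce.

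**Inputs**
- Starting share monitored, m0 = 0.46. Section 1.2.5 reports of the 56-hospital study that "we found that the overall monitoring rate across all hospitals was 46" percent. The population was stable children on room air.
- Range across hospitals in the same section: below 5% to above 85%.
- Share monitored after the intervention, m1: not in the documents; assumed at 30%, 20%, 10% and 5%.
- Assumption: activation risk is constant and does not depend on monitoring status.

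**Formula.** With A total activations and a share m monitored at the event, expected study adverse events = A × (1 − m). The ratio after to before is (1 − m1)/(1 − m0), and A cancels.

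| Monitored, from → to | Adverse events per 100 activations | Ratio |
|---|---|---|
| 46% → 30% | 54 → 70 | 0.70/0.54 = 1.30 |
| 46% → 20% | 54 → 80 | 0.80/0.54 = 1.48 |
| 46% → 10% | 54 → 90 | 0.90/0.54 = 1.67 |
| 46% → 5% | 54 → 95 | 0.95/0.54 = 1.76 |
| 85% → 46% | 15 → 54 | 0.54/0.15 = 3.6 |

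Total activations stay at 100 in every row.

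**Masking in the other direction.** For 46% to 20%, the count stays flat if total risk is multiplied by 0.54/0.80 = 0.675. Total risk could therefore fall by 32.5% with no fall in the count.

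**Comparison between hospitals, with no assumed end value.** At equal risk, a hospital monitoring 5% would label 95% of its activations as adverse events, and one monitoring 85% would label 15%. The ratio is 0.95/0.15 = 6.3 without any difference in safety.

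**Sensitivity to the population.** Surveillance covers all bronchiolitis patients, not only stable ones on room air. Let a share f of activations occur in stable room-air children, and let a share u of the others be unmonitored regardless of the intervention. The count per activation is then f(1 − m) + (1 − f)u. For 46% to 20%:
- f = 1: 0.80/0.54 = 1.48.
- f = 0.5, u = 0.10: 0.45/0.32 = 1.41.
- f = 0.2, u = 0.10: 0.24/0.188 = 1.28.

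Over f from 0.2 to 1 and u from 0 to 0.10, the ratio runs from 1.28 to 1.48. The size shrinks and the direction does not change.

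**The case against.** The strongest case on the other side is that this is a case-finding screen, not a rate. It targets the one harm pathway that the section names, and each flagged event gets an individual judgement from the chart and from staff. On that view the count carries no inference, and several stronger readings of the problem fail.

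- **A reader might infer that total activations are thrown away.** The plan does not say so. Every activation is ascertained and its chart reviewed, and section 8.4.1.1 retains all study information for 6 years. What is missing is a requirement to record and report the total.
- **A reader might infer that a successful hospital would be declared unsafe or stopped.** No threshold or comparison acts on the count, and suspension follows the Unanticipated Problem definition.
- **A reader might infer that delayed-detection cases are certain to be lost.** The test looks back to the event that led to the activation. In the example above, the hypoxia at the intermittent check can fairly be read as that event, with the child unmonitored at the time. The case is ambiguous, not excluded.
- **A reader might infer that the later cluster-randomized trial will inherit this measure.** Nothing in the documents says it will reuse the definition.
- **A reader might take the factors as forecasts.** They borrow a rate from a narrower population. Surveillance also runs only in the intervention period, after educational outreach has begun, so no before-count exists against which to see the rise.

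Section 7.2 also offers a route to the IRB for research-related problems that is not limited to unmonitored children.

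All of this limits the consequences. It does not remove the filter: section 7.2 prescribes no review or tabulation of activations in monitored children, and individual adjudication applies only to events that have already passed the filter.

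**Conclusion.** The point holds as a gap in what must be documented, assessed and reported. Section 8.4.1.2 conditions the adverse event label, the required record and the relatedness step on the variable that the intervention aims to change, and no other section requires the total or the monitored subset to be recorded.

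At unchanged risk the count would rise by a factor of about 1.3 to 1.8 for a fall in use from 46% to between 30% and 5%. This rests on equal activation risk by monitoring status, assumed end values, and the stable room-air rate applied to all bronchiolitis patients. The direction needs only that children moved off monitors have some activation risk.

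The practical consequence is moderate, because nothing in the plan acts on the count. The change is still worth making: the unmonitored subset alone cannot support the safety evaluation that the section promises, and the undefined term lets sites classify the same event differently.

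**What to change.** In section 8.4.1.2:

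1. Define unmonitored: no continuous pulse oximetry, no electrocardiographic monitoring, or neither.
2. Record every reviewed activation, with date, unit, monitoring status at the precipitating event and at the team call, and whether continuous oximetry had been stopped or not started earlier in that stay on a participating unit.
3. Apply the relatedness step to all activations in which it had been stopped or not started, not only to children unmonitored at the event.
4. Report total activations beside the unmonitored subset, with a denominator of bronchiolitis patients or patient-days on participating units.
5. Present this as descriptive. With one arm and no comparison period, even the full table cannot attribute a change to the intervention.

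At unchanged risk the total per patient-day would stay level while the unmonitored subset grew, so reclassification could be told apart from a change in overall risk.

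The cost is about one line per activation on charts already being reviewed, a census count for the denominator, and a few more events in relatedness review. No clinical rule changes.

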8.4.2 Risk Assessment

Risks are not greater than minimal in this study. The primary risk is breach of privacy and confidentiality. Less likely are threats to patient safety. These risks will be minimized as described above.

Given that there are national recommendations from Choosing Wisely and the AAP that support using less continuous monitoring in stable bronchiolitis, this study is not introducing any additional risk than would be introduced if clinical leaders initiated efforts into routine clinical care to align their hospitals’ practice with the existing national guidelines. The intervention simply aims to measure the feasibility of revealing how hospitals are doing with respect to these guidelines by showing them their own data, and providing information/education on the existing recommendations. All decisions about changes to monitoring are made by the primary medical team, not the researchers.

8.4.3 Potential Benefits of Trial Participation

8.4.3.1 Direct

Patients, their families, and the health professionals caring for them have the potential to benefit from higher quality, guideline-concordant health care. This may produce fewer monitor alarms, and thereby fewer interruptions from alarms that may break the concentration of health professionals and contribute to errors, wake patients from sleep, or cause unnecessary anxiety in patients and their loved ones. The patients also may have a lower risk of harm due to a reduction in the probability of the clinicians caring for them experiencing the alarm fatigue that can result from high alarm rates. Patients may also benefit by not having their hospital stays prolonged unnecessarily due to the overdiagnosis of inconsequential mild hypoxemia.

8.4.3.2 Indirect

The study outlined in this proposal will generate important knowledge that will advance (a) the science of audit and feedback and (b) plans for a future large-scale cluster-randomized trial of this intervention.

8.4.4 Risk-Benefit Assessment

Based on the discussion above and the lack of deviation from standard clinical care, the benefits of this study far outweigh the minimal risks. Given that the risks of the study are minimal, it is reasonable to proceed with the project.

8.5 Recruitment Strategy

The pragmatic approach to recruitment of health care professionals and patients for the intervention has been described in previous sections.

For the data collection in-person observational rounds, site investigators will identify all patients currently admitted to their hospital's non-ICU pediatric wards with bronchiolitis by reviewing the census of each unit that cares for children with bronchiolitis and examining the charts of patients meeting age criteria to determine if they are eligible. Eligibility screening does not involve recording any data until the patient is determined to be eligible and is enrolled.

For the primary objective, measuring feasibility, acceptability, and appropriateness using the validated questionnaire instruments, site PIs will distribute the questionnaire to the following health care professional types who worked on an intervention unit in a role involving the care of patients with bronchiolitis during the intervention period:

- Attending physicians
- Resident physicians
- Nurses
- Nursing assistants
- Physician assistants
- Respiratory therapists
- Other relevant staff (e.g. if a hospital's bronchiolitis care team includes staff who educate parents about their child's condition prior to discharge, we would include them here)

Questionnaires will be distributed in paper and electronic formats. Paper questionnaires will be distributed during unit-based events such as safety huddles,^{24,25} staff meetings, and rounds and subsequently entered into a CHOP-based REDCap form by the site investigative team or scanned and emailed to the CHOP-based study email address. Electronic questionnaires will be distributed using CHOP-based REDCap survey distribution tools to track responses and nonresponses. In order to distribute, site PIs will work with unit leadership within each discipline listed above to identify potential eligible health professional subjects. Site PIs will submit a list of email addresses of these potential subjects to CHOP study leadership, who will enter these into the CHOP-based REDCap survey distribution system.

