4.2 Intervention period

- Implementation teams will conduct data collection rounds and supplemental chart review (see Section 5) to determine continuous pulse oximetry status on bronchiolitis patients not receiving supplemental oxygen or room air flow, targeting data collection at least twice per week in order to acquire sufficient data for audit and feedback intervention.
- If any hospital staff responsible for the care of the patient are present and available on the unit, the data collector may perform real-time inquiry if feasible, briefly asking about the indications for monitoring individual patients, which will be documented in the study database as field notes without documenting any of the hospital staff member's identifiers.
- On a weekly basis, the data will be summarized in a dashboard and the dashboard along with the raw data will be returned to the site PI.
- Local implementation team will then share that data in electronic and in-person settings appropriate and tailored to each site (e.g. email, safety huddles,^{24,25} staff meetings, rounds, staff messages in electronic health record systems) with key clinician stakeholders who order or manage continuous pulse oximetry monitoring for bronchiolitis patients. Data will be contextualized with (a) the hospital's prior performance, (b) other hospitals' prior performance, (c) the current performance of other units in the same hospital, (d) the current performance of other units in other hospitals.
- Additional educational materials will be distributed and additional education/outreach sessions will be held by the local implementation team at a frequency determined by the site PI depending on local pulse oximetry use rates.

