5.4 Staff questionnaires (see appendix for instrument)

5.4.1 Site PIs will submit to CHOP for recruitment

- Email addresses of potential health professional subjects

5.4.2 The questionnaires will include the following elements:

- Hospital
- Unit(s) where person worked during the intervention period
- Profession (nurse, attending physician, etc.)
- Did the person care for any patients with bronchiolitis on an intervention unit during the intervention period?
- Gender, race, ethnicity of subject completing the questionnaire
- Acceptability of Intervention Measure (AIM)
- Intervention Appropriateness Measure (IAM)
- Feasibility of Intervention Measure (FIM)

- Supplemental items (see appendix)

Please note that we may make minor changes to the items included in the questionnaire in the months between initial IRB submission and questionnaire administration based on ongoing discussion with the investigative team and site PIs. As long as the changes do not represent major changes in scope, we will not submit revised versions of the questionnaire to the IRB.

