6.1 Primary Endpoint

The primary endpoints are the resulting scores on the questionnaire measures above.

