6.3 Statistical Methods

6.3.1 Questionnaire-based methods (AIM, IAM, FIM)

We will generate average scores for each item and for each measure, stratified by hospital and role (e.g. nurse, physician).

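### Paper questionnaires may be entered by site staff who overlap with the team delivering the intervention, so the primary ratings are open to upward courtesy bias of unknown size

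*Combined protocol and SAP*

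**What the plan says.** Section 6.1 sets the endpoint: "The primary endpoints are the resulting scores on the questionnaire measures above". These are the AIM, IAM and FIM. Section 6.3.1 analyses them as mean scores by hospital and role.

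Section 8.5 allows two formats.

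- **Paper:** "Paper questionnaires will be distributed during unit-based events such as safety huddles", staff meetings and rounds. Completed forms are "subsequently entered into a CHOP-based REDCap form by the site investigative team or scanned and emailed to the CHOP-based study email address".
- **Electronic:** "Electronic questionnaires will be distributed using CHOP-based REDCap survey distribution tools to track responses and nonresponses". Site PIs supply the email addresses.

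Section 5.1 describes electronic distribution only.

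Among the fields listed in 5.4.2 are hospital, profession, "Unit(s) where person worked during the intervention period" and "Gender, race, ethnicity of subject completing the questionnaire".

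On delivery of the intervention, section 4.2 says: "Local implementation team will then share that data in electronic and in-person settings appropriate and tailored to each site". Huddles, staff meetings and rounds are among its examples. The site PI receives the weekly dashboard and decides how often further outreach takes place.

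Section 8.4.1.1 provides that everything submitted to CHOP goes back to the site PI when the study ends, so that sites can meet local retention rules. It makes no exception for questionnaires.

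**The concern.** AIM, IAM and FIM are opinions about a strategy that local colleagues or seniors have championed. A respondent who is given a form at a huddle, and who knows or suspects that the local team will read it, has a reason to be polite. The likely direction is upward, which favours the intervention. Collecting more forms does not remove such a shift.

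If hospitals differ in their use of paper, part of the difference between hospital means could come from the collection mode. The scores are meant to inform a later cluster-randomized trial, and nothing in the plan would show whether a shift had occurred.

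**Working it through.** **1. Do the people handling forms have a stake in the answers?** Section 8.5 names the site investigative team for data entry. Section 4.2 names the local implementation team for delivery. No sentence equates the two. However, 4.2 gives the data collection rounds to the implementation teams and 5.1 gives the same rounds to site investigators, and the site PI has a part in delivery. The groups overlap. For the scan-and-email option, 8.5 does not say who scans.

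**2. Can a respondent be recognised?** Section 3.3.2 plans with 5 units per hospital, a nominal 100 staff per unit and a target of 100 questionnaires per hospital. Section 8.5 lists seven staff categories.

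- Forms per unit: 100 / 5 = 20.
- Forms per unit and category, on average: 20 / 7 = about 2.9.
- Staff per unit and category, on average: 100 / 7 = about 14, before splitting by gender, race and ethnicity.

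These averages hide the uneven mix. Nurses will be well above them and some professions well below. Recognition is plausible in small professions and less so among nurses.

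**3. Is there a safeguard?** Section 8.3 says the questionnaires hold no PHI and that site personnel may use study records only to conduct the study. The first concerns health information and the second limits misuse. Neither prevents a colleague from reading a form. No sealed return, independent entry or analysis by mode is described. By contrast, 5.3.1 requires the method of bedside observation to be recorded. The fields in 5.4.2 have no equivalent for questionnaire mode.

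**4. How large could a shift be?** First, the plan's own figures. Section 6.4 tests 4.0 against 3.0 with SD 3 and alpha 0.05 (taken as two-sided), using power = Phi(difference × √n / SD − 1.96).

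- n = 100: 1.0 × 10 / 3 = 3.33, power 91.5% (91.0% by the noncentral t). Stated: 90%.
- n = 73: 1.0 × 8.544 / 3 = 2.85, power 81.3% (80.2% by the noncentral t). Stated: 80%.

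Both reproduce.

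Next, an illustration. Shift in a hospital mean = paper share × shift per paper form. **Both inputs are assumptions; the documents supply neither.** With SD 3 and n = 100 the standard error is 3 / 10 = 0.30. If the true mean is 3.0, the chance of wrongly concluding in favour (nominally 2.5%, noncentral t) is:

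| Paper share (assumed) | Shift per form (assumed) | Shift in mean | False favourable result |
|---|---|---|---|
| 25% | 0.25 | 0.0625 | 4.0% |
| 50% | 0.50 | 0.25 | 12.8% |
| 100% | 0.50 | 0.50 | 37.8% |

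With an assumed SD of 1, which the protocol does not state, the three figures would be 9.0%, 69.7% and 99.9%. The spread shows how far the answer depends on unknown inputs. It is not an estimate.

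**The case against.** Four arguments carry weight.

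- **Paper may be a small supplement.** Section 5.1 mentions electronic distribution only, and 5.4.1 collects email addresses. This stands: no paper share can be assumed as fact.
- **A modest shift would not overturn a clear result.** Even the largest shift in the table turns an observed 4.0 into 3.5, still above 3.0. This stands under those assumptions.
- **This is a feasibility pilot.** Section 6 puts little weight on power, and 6.3.1 plans descriptive means. This limits the severity, but a mean can be biased whether or not it is tested.
- **Respondents may be promised confidentiality.** The consent wording and draft items sit in the eIRB application, not in the protocol, so this cannot be judged. A promise would not change who handles the forms under 8.5.

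A reader might also infer more than the text supports:

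- *That the electronic route is free of the problem.* It avoids site handling at collection, but 8.4.1.1 sends all submitted data back to the site PI.
- *That the team entering forms is the team that ran the intervention, and that it sees every paper answer.* Overlap is shown, identity is not, and the scanner is unnamed.
- *That the scores will be inflated, or that hospitals using more paper will look better.* The documents support a risk with a likely direction, not a demonstrated effect.

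**Conclusion.** The concern holds as a risk. Ratings on paper forms that site personnel may enter, with fields that can identify staff in small professions, are open to upward courtesy bias in the primary endpoint. The plan can neither detect nor bound it. The size cannot be estimated from the documents.

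The conclusion rests on the overlap of teams inferred from 4.2 and 5.1, and on the ordinary expectation that people rate more kindly when colleagues may read the answer. It is a cheap improvement rather than a flaw that undermines the study. It has to be made before questionnaires go out, because analysis cannot recover lost candour.

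**What to change.** - **8.5:** Bar site personnel from viewing or entering completed questionnaires. At unit events, offer a code or tablet link to the central REDCap survey, or collect paper in sealed envelopes sent unopened to the coordinating centre for entry. Bring 5.1 into line on the formats used.
- **8.4.1.1:** Exempt individual-level questionnaire data from return to the site PI, or return them only in aggregate or without unit and demographic fields, subject to local retention rules. Without this change, an assurance given under 8.5 would be untrue.
- **Opening text of the questionnaire:** Tell respondents who will and will not see their answers.
- **5.4.2 and 6.3.1:** Record paper or electronic mode and report mean scores by mode. Staff are not randomized to a mode, so the comparison is descriptive: it can flag a shift but not prove its cause.

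The cost is envelopes and postage or a survey link, some central data entry, slightly slower return and possibly a few fewer paper forms.
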